#### 14.2.5 UNANESTHETIZED SCHIRMER'S TEST

Unanesthetized Schirmer's Test will be assessed on both eyes post-CAE at Visits 1, 2, 4, 5, and 6. The Schirmer's test strip will be placed in the lower temporal lid margin of each eye. After 5 minutes, the test strip will be removed and the length of the moistened area will be recorded in millimeters (mm) for each eye. Lower values indicate less tears produced in the eye.

Unanesthetized Schirmer's Test will be summarized by visit using quantitative summary statistics. Change from baseline will be also summarized.

Pairwise two-sample t-tests will be employed to compare treatment and placebo means at each visit. Comparisons between treatment groups and between all active groups and placebo will also be conducted. The differences in means, two-sided 95% confidence intervals (CIs) for the difference in means and p-values will be reported. Wilcoxon rank sum tests will also be conducted. Analyses will be performed on the ITT population with observed data only.

Changes from baseline will be compared between treatment groups using ANCOVA models that adjust for baseline and site. The differences in means, two-sided 95% confidence intervals (CIs) for the difference in means and p-values will be reported. T-tests and Wilcoxon rank sum tests will also be conducted. Analyses will be performed on the ITT population with observed data only.

#### **14.2.6 ORA CALIBRA® OCULAR DISCOMFORT SCALE**

Ocular discomfort scores will be subjectively graded by the subjects using the Ora Calibra® Ocular Discomfort Scale at all scheduled visits. Both pre- and post-CAE® assessments will be made at Visits 1, 2, 4, 5, and 6. Ocular discomfort scores will also be assessed during the CAE® exposure, immediately upon entering the chamber and [REDACTED]

[REDACTED] The ocular discomfort scale ranges from 0 to 4 where [REDACTED]

##### **14.2.6.1 ORA CALIBRA® OCULAR DISCOMFORT SCALE PRE-, POST-, AND NON-CAE®**

Pre- and post-CAE® assessments of ocular discomfort will be made at Visits 1, 2, 4, 5, and 6. Ocular discomfort will also be assessed during the non-CAE Visit 3. Continuous descriptive statistics, including 95% CIs, as well as changes from baseline will be summarized by treatment group, visit and time point. Pairwise two-sample t-tests will be employed to compare treatment and placebo means at each visit and time point. Comparisons between treatment groups and between all active groups and placebo will also be conducted. The differences in means, two-sided 95% confidence intervals (CIs) for the difference in means and p-values will be reported. Wilcoxon rank sum tests will also be conducted. Analyses will be performed on the ITT population with observed data only.

Changes from baseline will be compared between treatment groups using ANCOVA models that adjust for baseline and site. The differences in means, two-sided 95% confidence intervals (CIs) for the difference in means and p-values will be reported. T-tests and Wilcoxon rank sum tests will also be conducted. Analyses will be performed on the ITT population with observed data only.

##### **14.2.6.2 ORA CALIBRA® OCULAR DISCOMFORT SCALE DURING CAE® EXPOSURE**

Ocular discomfort scores will be assessed [REDACTED] during the CAE® exposure. Continuous descriptive statistics, including 95% CIs, as well as changes from baseline will be summarized by

treatment group, visit, and time point. The change from the 0 minutes assessment within the same visit and changes from baseline will also be summarized by treatment group, visit, and time point.

For both the ocular discomfort score and the change from 0 minutes, Pairwise two-sample t-tests will be employed to compare treatment and placebo means at each visit and time point. Comparisons between treatment groups and between all active groups and placebo will also be conducted. The differences in means, two-sided 95% confidence intervals (CIs) for the difference in means and p-values will be reported. Wilcoxon rank sum tests will also be conducted. Analyses will be performed on the ITT population with observed data only.

Changes from baseline will be compared between treatment groups using ANCOVA models that adjust for baseline and site. The differences in means, two-sided 95% confidence intervals (CIs) for the difference in means and p-values will be reported. T-tests and Wilcoxon rank sum tests will also be conducted. Analyses will be performed on the ITT population with observed data only.

#### **14.2.7 ORA CALIBRA® OCULAR DISCOMFORT & 4-SYMPOTM QUESTIONNAIRE**

Ocular discomfort and dry eye symptoms will be assessed at all scheduled visits at the subject level in regard to how both eyes feel. Both pre- and post-CAE® assessments will be made at Visits 1, 2, 4, 5, and 6. Subjects will also grade the severity of their dry eye syndrome symptoms each day during the at-home dosing period in their diary in the morning and in the evening, before instilling the study drug. The Ora Calibra® Ocular Discomfort & 4-Symptom Questionnaire will be used, which includes rating of the severity of 5 symptoms: ocular discomfort, burning, dryness, grittiness, and stinging. Each symptom rating ranges from 0 to 5, where [REDACTED].

##### **14.2.7.1 ASSESSMENTS DURING VISITS**

Ocular discomfort and dry eye symptoms will be summarized by visit, time point, and treatment group using quantitative summary statistics including 95% CIs. Change from baseline will be also summarized. Pairwise two-sample t-tests will be employed to compare treatment and placebo means as well as the changes from baseline at each visit and time point. Comparisons between treatment groups and between all active groups and placebo will also be conducted. The differences in means, two-sided 95% confidence intervals (CIs) for the difference in means and p-values will be reported. Wilcoxon rank sum tests will also be conducted. Analyses will be performed on the ITT population with observed data only.

Changes from baseline will be compared between treatment groups using ANCOVA models that adjust for baseline and site. The differences in means, two-sided 95% confidence intervals (CIs) for the difference in means and p-values will be reported. T-tests and Wilcoxon rank sum tests will also be conducted. Analyses will be performed on the ITT population with observed data only.

#### 14.2.7.2 DIARY ASSESSMENTS

Each day during the at-home dosing period (including the run-in period), subjects will grade the severity of their dry eye symptoms in their diary in the morning and evening, before instilling the study drug. The average of the morning and evening assessments will be calculated for each day and symptom.

The worst symptom for each subject will be identified as the symptom with the highest average score during the run-in period (Days -14 to -1) as recorded in the subject diary. First daily averages, per symptom, from morning and evening diary entries will be calculated. Then the daily averages will be averaged for each symptom. The highest average symptom is called the worst symptom for each subject.

The worst symptom and each individual symptom will be summarized by day, time point (morning and evening), and treatment group using quantitative summary statistics including 95% CIs. The average post-treatment score for the worst symptom and each individual symptom will also be summarized by time point and treatment group. Change from baseline will be also summarized. Pairwise two-sample t-tests will be employed to compare treatment and placebo means as well as the changes from baseline at each day and time point. Comparisons between treatment groups and between all active groups and placebo will also be conducted. The differences in means, two-sided 95% confidence intervals (CIs) for the difference in means and p-values will be reported. Wilcoxon rank sum tests will also be conducted. Analyses will be performed on the ITT population with observed data only.

Changes from baseline will be compared between treatment groups using ANCOVA models that adjust for baseline and site. The differences in means, two-sided 95% confidence intervals (CIs) for the difference in means and p-values will be reported. T-tests and Wilcoxon rank sum tests will also be conducted. Analyses will be performed on the ITT population with observed data only.

Daily average scores of ocular discomfort, each individual symptom and worst symptom will be displayed graphically by day in a line plot by treatment group.

#### 14.2.8 VISUAL ANALOGUE SCALE

At every visit, subjects will be asked to rate each ocular symptom due to ocular dryness by placing a vertical mark on a horizontal line of length 100 mm to indicate the level of discomfort. 0 mm corresponds to "no discomfort" and 100 mm corresponds to "maximal discomfort." Both pre- and post-CAE® assessments will be made at Visits 1, 2, 4, 5, and 6. Symptoms assessed are burning/stinging, itching, foreign body sensation, blurred vision, eye dryness, photophobia, and pain.

Symptom scores will be summarized by visit, time point, and treatment group using quantitative summary statistics, including 95% confidence intervals. Change from baseline will also be summarized.

Pairwise two-sample t-tests will be employed to compare treatment and placebo means at each visit and time point. Comparisons between treatment groups and between all active groups and placebo will also be conducted. The differences in means, two-sided 95% confidence intervals (CIs) for the difference in means and p-values will be reported. Wilcoxon rank sum tests will also be conducted. Analyses will be performed on the ITT population with observed data only.

Changes from baseline will be compared between treatment groups using ANCOVA models that adjust for baseline and site. The differences in means, two-sided 95% confidence intervals (CIs) for the difference in means and p-values will be reported. T-tests and Wilcoxon rank sum tests will also be conducted. Analyses will be performed on the ITT population with observed data only.

#### 14.2.9 OCULAR SURFACE DISEASE INDEX®

The OSDI® is assessed on a scale of 0 to 100, with higher scores representing greater disability. The OSDI® asks the following 12 questions at the subject level:

Have you experienced any of the following during the last week:

- 1) Eyes that are sensitive to light?
- 2) Eyes that feel gritty?
- 3) Painful or sore eyes?
- 4) Blurred vision?
- 5) Poor vision?

Have problems with your eyes limited you in performing any of the following during the last week:

- 6) Reading?
- 7) Driving at night?
- 8) Working with a computer or bank machine (ATM)?
- 9) Watching TV?

Have your eyes felt uncomfortable in any of the following situations during the last week:

- 10) Windy conditions?
- 11) Places or areas with low humidity (very dry)?
- 12) Areas that are air conditioned?

OSDI® will be collected for both eyes pre-CAE® at each visit. The 5-unit scale for responses to the OSDI® is given by the following: 0=None of the time, 1=Some of the time, 2=Half of the time, 3=Most of the time and 4>All of the time. The total OSDI® score is calculated by the following:

$$\text{OSDI}^{\circledR} = \frac{(\text{sum of scores}) \times 25}{\text{_____}}$$

## # of questions answered

Note that the number of questions answered in the denominator should exclude those questions with a response of "N/A". Continuous descriptive statistics, including 95% CIs, as well as changes from baseline will be summarized by treatment group and visit. Each individual response and the total OSDI® score will be presented separately.

Pairwise two-sample t-tests will be employed to compare treatment and placebo means at each visit. Comparisons between treatment groups and between all active groups and placebo will also be conducted. The differences in means, two-sided 95% confidence intervals (CIs) for the difference in means and p-values will be reported. Wilcoxon rank sum tests will also be conducted. Analyses will be performed on the ITT population with observed data only.

Changes from baseline will be compared between treatment groups using ANCOVA models that adjust for baseline and site. The differences in means, two-sided 95% confidence intervals (CIs) for the difference in means and p-values will be reported. T-tests and Wilcoxon rank sum tests will also be conducted. Analyses will be performed on the ITT population with observed data only.

**14.2.10 ORA CALIBRA® DROP COMFORT ASSESSMENT**

Drop comfort will be assessed for each eye immediately, and at 1 and 2 minutes following initial dosing at Visit 2 using the Ora Calibra® Drop Comfort Scale. The scale ranges from 0 to 10, with 0 indicating very comfortable and 10 indicating very uncomfortable. Drop comfort will be summarized by time using quantitative summary statistics. Pairwise two-sample t-tests will be employed to compare treatment and placebo means. Comparisons between treatment groups and between all active groups and placebo will also be conducted. The differences in means, two-sided 95% confidence intervals (CIs) for the difference in means and p-values will be reported. Wilcoxon rank sum tests will also be conducted. Analyses will be performed on the ITT population with observed data only.

Descriptions of drop comfort will be assessed at [REDACTED] following initial dosing at Visit 2 using the Ora Calibra® Drop Comfort Questionnaire. On this questionnaire, subjects will be asked to choose three words that best describe how each eye drop feels in both of his/her eyes. The positive responses are comfortable, cool, refreshing, smooth, and soothing. The negative responses include burning, filmy, stinging, sticky, thick, gritty, and irritating. Subjects may also select "other" and write in a response of their choosing, which may be either a positive or a negative response. Drop Comfort Questionnaire responses will be summarized by treatment group using qualitative summary statistics. Subjects with at least one negative response will also be summarized by treatment group. Analyses will be performed on the ITT population with observed data only.

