8.3 EXAMINATION PROCEDURES

An ICF must be signed and dated by the subject, the PI or designee and witness (if required) before any study-related procedures are performed.

Procedures listed below should be performed in the given order. See **Appendix 2** for details on methodologies and grading systems.

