- Drop Comfort Assessment A drop comfort evaluation will be performed immediately and then at 1, 2 and 3 minutes following initial dosing.
- Monitoring and Query of AEs
- Study Drug Diary/Study Drug Dispensation Prior to discharge from the study site on Visit 2 (Day 1), randomized subjects will be educated in study drug diary recording and self-administration of study drug. Subjects will receive their assigned study drug kit with sufficient supply to last until Visit 3 and will be instructed NOT to self-administer study drug on the morning of their next scheduled study visit (Visit 3, Day 8).
- Schedule Next Visit Subjects will be scheduled for Visit 3.

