## 5. Study Treatments

### 5.1 Method of Assigning Subjects to Treatment Groups

Prior to initiation of study run-in (at Visit 1), each subject who qualifies for entry will be assigned a screening number. All screening numbers will be assigned in strict numerical sequence at a site and no numbers will be skipped or omitted. If all inclusion and exclusion criteria are met at Visits 1 and 2, each qualifying subject will then be assigned a randomization number at the end of Visit 2.

A randomization schedule will be generated using block randomization. Blocks of randomization numbers will be distributed to sites, such that there will be an approximate equal number of subjects assigned to each of the three treatment arms at each site. The site staff will dispense to the patient the study kit labeled with the corresponding randomization number. The randomization number will be recorded on the patient's source document and eCRF. A new kit will be dispensed at Visits 2, 4, and 5 based on the subject's randomization. The Visit 2 kit will be re-dispensed at Visit 3. The Sponsor, Investigators, and study staff will be masked during the randomization process and throughout the study.

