## **9. General Statistical Considerations**

### **9.1 Unit of Analysis**

Safety endpoints will be analyzed for both eyes. For efficacy endpoints, the unit of analysis will be the study eye, or the “worst eye,” as defined by the following:

**Study Eye/Worst Eye:** Eyes are eligible for analysis if they meet all of the inclusion criteria. In the case that both eyes are eligible for analysis, the worst eye will be the eye with worse (higher) inferior corneal staining pre-CAE® at Visit 2. If the inferior corneal staining is the same in both eyes, then the worst eye will be the eye with the highest ocular discomfort pre-CAE® at Visit 2. If the ocular discomfort is the same in both eyes, then the right eye will be selected as the worst eye.

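### Drop comfort is tested without covariates although site and a same-eye pre-dose discomfort score are available; an added ANCOVA may improve precision at almost no cost

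*SAP*

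**What the plan says.** **Planned tests.** SAP 14.2.10 gives the comparison of each dose with placebo as "Pairwise two-sample t-tests will be employed to compare treatment and placebo means" and adds "Wilcoxon rank sum tests will also be conducted". It also compares the two doses with each other and the pooled doses with placebo. It names no covariate and no site term.

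**Timing and unit.** The SAP says: "Drop comfort will be assessed for each eye immediately, and at 1 and 2 minutes following initial dosing at Visit 2". The scale runs from 0 to 10. Protocol 8.3.2 says: "A drop comfort evaluation will be performed immediately and then at 1, 2 and 3 minutes following initial dosing". The SAP's time for the separate Drop Comfort Questionnaire is blacked out, so the extra minute in the protocol cannot be read as a contradiction. Drop comfort is listed both as a secondary efficacy endpoint (SAP 3.2) and as a safety variable (SAP 3.3).

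**Candidate covariates.** On the Ocular Discomfort Scale, SAP 14.2.6 says: "Both pre- and post-CAE® assessments will be made at Visits 1, 2, 4, 5, and 6". The score is held per eye, since the tie-break in SAP 9.1 compares the two eyes: "If the ocular discomfort is the same in both eyes, then the right eye will be selected as the worst eye". On site, SAP 5.1 says: "Blocks of randomization numbers will be distributed to sites". The protocol synopsis allows up to 3 sites.

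**Other secondary endpoints.** SAP 14.2.1 to 14.2.9 give the staining, TFBUT, redness, Schirmer's, discomfort, symptom, VAS and OSDI endpoints an ANCOVA of change from baseline, with baseline and site as covariates. Tear mediators (SAP 14.2.12) get only t-tests and Wilcoxon tests. Protocol 10.4.6 permits an ANCOVA for secondary variables where it is suitable, and names t-tests and Wilcoxon tests in a list that includes drop comfort.

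**The concern.** The first randomized drop goes into an eye that has been through the CAE at the same visit. How uncomfortable that eye already was could plausibly affect how the drop is rated, and subjects will differ in this. If so, part of the spread in drop comfort is predictable from a score taken before randomization, and an unadjusted test leaves that part in the error term. Any difference in rating level between sites also stays there, even though allocation is balanced within site.

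At stake is the precision of the comparison of each dose with placebo on how the drop feels. Each eye is rated at several times, but all of them follow one dose at one visit, so no later visit can make up for an imprecise result.

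**Working it through.** **1. The plan's own power figures.** No SD, effect or power target is given for drop comfort. The only power statement (SAP 6, protocol 10.3) is for the co-primary endpoints at 45 per arm, two-sided 0.05. With power = Φ(δ / (SD·√(2/n)) − 1.96):
- Sign: 0.5 / (0.72 × √(2/45)) = 3.29, power 0.909 (0.903 with the noncentral t).
- Symptom: 0.80 / (1.15 × √(2/45)) = 3.30, power 0.910 (0.904 with the noncentral t).

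Both agree with the stated 90%. So do 0.9² = 0.81, 0.9⁴ = 0.656 and 45 / 0.90 = 50.

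**2. Inputs for drop comfort.**
- From the documents: 50 per arm (the rating is made on the day of randomization, before dropout), two-sided 0.05, up to 3 sites.
- Assumed: r, the within-site correlation of the post-CAE discomfort score with drop comfort, from 0 to 0.5; ICC, the share of drop comfort variance lying between sites, from 0 to 0.10.
- Drop comfort is expressed in SD units.

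**3. Unadjusted t-test.** Degrees of freedom are 98. The 95% CI half-width is t(0.975, 98) × √(2/50) = 0.397 SD. The difference detectable with 80% power is 0.566 SD, which serves as the reference effect.

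**4. ANCOVA with the discomfort score and site.** Degrees of freedom are 100 − 5 = 95 (intercept, treatment, score, two site terms).
- Residual variance v = (1 − ICC)(1 − r²).
- SE = √(v × 2/50 × (1 + 1/94)); the last factor is the small-sample cost of estimating the slope.
- Half-width = t(0.975, 95) × SE.
- Example, r = 0.5 and ICC = 0.10: v = 0.90 × 0.75 = 0.675, SE = 0.165, half-width 0.328, ratio 0.328 / 0.397 = 0.826.

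| ICC | r | v | Half-width (SD) | Ratio to 0.397 | Power at 0.566 SD |
|---|---|---|---|---|---|
| 0 | 0 | 1.000 | 0.399 | 1.006 | 79.6% |
| 0 | 0.1 | 0.990 | 0.397 | 1.001 | 80.0% |
| 0 | 0.2 | 0.960 | 0.391 | 0.985 | 81.1% |
| 0 | 0.3 | 0.910 | 0.381 | 0.959 | 83.2% |
| 0 | 0.5 | 0.750 | 0.346 | 0.871 | 89.6% |
| 0.05 | 0 | 0.950 | 0.389 | 0.980 | 81.5% |
| 0.05 | 0.3 | 0.864 | 0.371 | 0.935 | 85.0% |
| 0.05 | 0.5 | 0.712 | 0.337 | 0.849 | 91.0% |
| 0.10 | 0 | 0.900 | 0.379 | 0.954 | 83.6% |
| 0.10 | 0.3 | 0.819 | 0.361 | 0.910 | 86.8% |
| 0.10 | 0.5 | 0.675 | 0.328 | 0.826 | 92.4% |

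**5. Simulation check.** 4,000 trials per setting were run with a rounded 0–10 score and allocation balanced within 3 sites. Power, unadjusted against adjusted:
- r = 0, ICC 0: 78.8% and 78.4%
- r = 0.2, ICC 0: 79.4% and 80.1%
- r = 0.3, ICC 0: 79.8% and 82.7%
- r = 0.5, ICC 0: 78.2% and 88.0%
- r = 0.5, ICC 0.05: 79.1% and 89.1%

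Type I error was between 4.2% and 5.9% for both tests over all settings. At r = 0.3 and ICC 0.05 it was 4.2% unadjusted and 5.0% adjusted, so ignoring site makes the t-test slightly conservative, not liberal.

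**The case against.** The strongest case on the other side is that this is a preference and not a fault. Four arguments support it.

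- **No shown loss.** A reader might infer that the plan certainly loses power. The documents do not support that, because they give no r, no ICC and no drop comfort SD. With r of 0.1 or less and no site effect there is nothing to gain. This stands, and it is why the size is given only as a range.
- **The score is not taken just before the drop.** Protocol 8.3 says: "Procedures listed below should be performed in the given order". Under 8.3.2 the post-CAE discomfort score is followed by the other questionnaires, slit lamp, redness, TFBUT, both dyes, Schirmer's test, eligibility review and a blood draw. By Appendix 2, the fluorescein wait (3–5 minutes) and the Schirmer's strip (5 minutes) alone take 8 to 10 minutes. In addition, every randomized subject has passed a discomfort threshold during the CAE, which may narrow the range of a 0–4 score. Both could lower r. This also stands, although the score still precedes randomization and is a legitimate covariate.
- **No inconsistency.** A reader might infer that drop comfort alone is denied an ANCOVA. It is not, since tear mediators have none either. The ANCOVAs elsewhere model change from the endpoint's own baseline, which drop comfort lacks. That explains why the template was not copied. It is no reason to omit site or a related pre-dose score.
- **Conformity with the protocol.** Protocol 10.4.6 names the t-test and Wilcoxon test for drop comfort, and SAP 17 declares no changes. Replacing the t-test would therefore be a departure. Adding an ANCOVA is not, because the same protocol section permits one, and the SAP already uses ANCOVA for staining, TFBUT and OSDI, which stand in the same list.

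**Conclusion.** The point holds as a minor matter of efficiency. The drop comfort comparison ignores a design factor (site) and a same-eye score recorded before dosing, and so may be less precise than the collected data allow.

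Over the assumed range the trade is lopsided. If neither covariate is prognostic, the interval widens by about 0.6% and power falls by 0.4 points. At r = 0.5 and ICC = 0.10 the interval narrows by about 17% and 80% power becomes about 92%. Where the truth lies cannot be settled from the documents, and the 80% starting power is itself only a reference.

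A reader might go further and infer that the t-test is invalid or that the trial's conclusions are at risk. Neither follows. Type I error stays near 5%, drop comfort has no power target, and the success rule (SAP 9.5) rests only on the primary sign and symptom in a trial that the SAP describes as mainly exploratory.

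**What to change.** In SAP 14.2.10, add an ANCOVA of study-eye drop comfort at each Drop Comfort Scale time point, with treatment, site and the same-eye Visit 2 post-CAE Ocular Discomfort score as terms. Report differences with 95% confidence intervals. Specify it before unmasking, so that it cannot be taken for a post hoc choice. Keep the two-sample t-test and the Wilcoxon rank sum test, both named in protocol 10.4.6, as supportive analyses.

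The cost is a short SAP revision and one more model to program. No new data are needed. The statistical cost is up to three degrees of freedom (two for site, one for the score) and the very slight widening shown above if neither covariate turns out to be prognostic.
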